10.3 DEMOGRAPHICS AND BASELINE CHARACTERISTICS

Subject demographics (age, race/ethnicity and gender) will be summarized by study group for the ITT, AT, and Safety populations using descriptive statistics. Age will be summarized as a continuous variable and categorized into the four groups based on the observed quartiles.

The baseline medicated IOP and washout (unmedicated) IOP will be summarized by study groups for the ITT and AT populations. They will be treated as continuous variables. The number of glaucoma medications in use at enrollment will be prepared for each of the study groups using descriptive statistics for categorical variables.

Medical and Ocular history will be summarized for each study group by number and percentage of subjects in the ITT and AT population.

For the Safety Population, ITT, and AT populations, subject accountability will be prepared based on Table G.1 of ANSI Z80.27-2014.

10.4.1

[REDACTED]

[REDACTED]

[REDACTED]

[REDACTED]

[REDACTED]

[REDACTED]

[REDACTED]

[REDACTED]

10.4.2 SENSITIVITY ANALYSIS

A tipping-point analysis will be performed for the primary effectiveness endpoint. Let n and m be the number of OMNI and iStent inject subjects that do not have the 12-month washed out DIOP due to any reasons other than the first four criteria listed in Section

[10.4.1.](#) [REDACTED]

[REDACTED]

10.4.3 COVARIATE ANALYSIS

The following variables will be examined for their prognostic value to the primary effectiveness endpoint using the AT population with the imputation used for the primary analyses:

- Age group (based on observed quartiles)
- Gender (male and female)
- Race/ethnicity
- Baseline unmedicated DIOP group (based on observed quartiles)
- Number of ocular hypotensive medications at screening
- Study Site

For the primary effectiveness endpoint, two-way ANOVA with study group (three groups), one of the factors listed above, and the interaction between the study group and the factor will be used to check the possible covariate effects. A p-value of 0.15 will be used for evaluating the possible covariate effects. It should be noted that the subgroups of these covariates will be re-examined and may be re-categorized or eliminated due to small sample size (if there are < 10 subjects within each subgroup).

The scatter plots of the 12-month unmedicated DIOP versus the baseline unmedicated DIOP along with a 45° line will be provided. The scatter plot of the percent change in unmedicated DIOP from baseline to 12 months versus the baseline unmedicated DIOP will also be provided. The Box plots of the change and percent change in unmedicated DIOP from baseline to 12 months will be prepared for each category of the covariates (except for the study site).

10.4.4 OTHER EFFECTIVENESS ENDPOINTS

The statistical analyses for the other effectiveness endpoints will be based on the available data of the AT population. The percent change in unmedicated DIOP from baseline at 12 months will be calculated for each study eye as

$$\% \text{ change} = \frac{(12\text{-month unmedicated DIOP} - \text{Baseline unmedicated DIOP})}{(\text{Baseline unmedicated DIOP})} \times 100\%.$$

The number and percent of subjects achieving $\geq 20\%$ reduction in unmedicated DIOP from baseline at 12 months (i.e., 12-month responder) will be calculated. The exact 95% confidence interval of the 12-month responder rate will be calculated by the binomial distribution for each study group separately. The difference in the 12-month responder between OMNI (canaloplasty AND trabeculotomy) and iStent inject groups and the corresponding 95% confidence interval per normal distribution will be calculated. The same statistics will be provided for the difference in the 12-month responder between OMNI (canaloplasty alone) and iStent inject groups. The same statistical methods will be used to summarize the subjects with an unmedicated DIOP between 6 and 18 mmHg

inclusive at 12 months.

The descriptive statistics for the continuous variables will be used to summarize the change in number of ocular hypotensive medications used from screening to 12 months. The ANOVA with study treatment group (three groups) as the factor will be used to compare the mean difference in the change in number ocular hypotensive medications used from screening to 12 months. The mean difference between OMNI (canaloplasty AND trabeculotomy) and iStent inject groups and that between OMNI (canaloplasty alone) and iStent inject groups will be evaluated using Dunnett's test. The same methods will be used to analyze the percent change in unmedicated DIOP from baseline to 12 months.

The analyses described in this section are exploratory in nature.

[REDACTED]

[REDACTED]

[REDACTED]

10.4.5 [REDACTED]

[REDACTED]

[REDACTED]

[REDACTED]

[REDACTED]

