8.4.6 MONTH 12 (DAYS 330 TO 420)

The Month 12 visit is the final visit for any subjects that are not currently on any ocular hypotensive medications. For patients on medications, all assessments except the DIOP will be completed (listed below for 9 am), however, depending on the medications used, will return in from 5 to 30 days following medication washout for the DIOP assessment.

[figure not shown]

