8.7 SECONDARY SURGICAL INTERVENTIONS TO CONTROL IOP

If the subject requires another glaucoma procedure (surgical or laser) to control their IOP, the subject should continue to be followed according to standard of care until the AE that required the surgical treatment resolves or 1-month post-re-intervention, whichever is longer. Following this, the subject should be withdrawn from the study.

Subjects who have a secondary IOP-lowering intervention will be considered treatment failures for the purpose of the effectiveness evaluation. For the primary effectiveness endpoint of the study, the corresponding baseline unmedicated DIOP will be used to impute the 12-month unmedicated DIOP. These subjects will be included in the Safety Endpoint analyses through their withdrawal from the study.

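### Section 10.4.4 analyses the responder endpoints and percent change in DIOP on available data, which does not carry through the treatment-failure status that section 8.7 gives to re-intervened subjects

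*Combined protocol and SAP*

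**What the plan says.** Section 10.4.4 sets the data basis for the exploratory endpoints: "The statistical analyses for the other effectiveness endpoints will be based on the available data of the AT population". These include the proportion with at least a 20% reduction in unmedicated DIOP, the proportion with DIOP from 6 to 18 mmHg, and percent change in DIOP. The readable text of that section does not mention re-intervention, failure status, imputation or the denominator.

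Section 8.7 states: "Subjects who have a secondary IOP-lowering intervention will be considered treatment failures for the purpose of the effectiveness evaluation". Follow-up after the second procedure is by standard of care until the adverse event "resolves or 1-month post-re-intervention, whichever is longer". Then: "Following this, the subject should be withdrawn from the study". The only numeric rule is this one: "For the primary effectiveness endpoint of the study, the corresponding baseline unmedicated DIOP will be used to impute the 12-month unmedicated DIOP".

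Section 10.4.3, the covariate analysis of the primary endpoint, says explicitly that it carries the primary-analysis imputation. Section 10.4.4 has no such wording.

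The synopsis and 10.4.4 both call these endpoints exploratory, and the synopsis says that they do not decide study success. Section 10.4.1, text at the end of 10.4.4, and 10.4.5 are blacked out.

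**The concern.** The failure sentence in 8.7 is not limited to the primary endpoint, yet the data rule in 10.4.4 does not carry it through. An analyst who programs 10.4.4 as written would produce two effects.

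- A re-intervened subject who was withdrawn without a 12-month DIOP leaves both responder denominators and the percent-change mean. Because the value is missing as a result of treatment failure, leaving the subject out is informative.
- A subject re-intervened late may still be in the study when the Month 12 window opens. A DIOP taken then reflects the second procedure, but it is available data and could be counted as a response to the randomised device.

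Both effects raise the reported responder rate. Section 10.4.4 plans exact confidence intervals for each arm's rate, and between-arm differences with intervals, so it matters who is in the denominator.

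**Working it through.** **Design figure.** With 137 completers per group and 10% drop-out, 137 / 0.9 = 152.2, rounded up to 153 per group, and 3 × 153 = 459. This matches the synopsis and leaves 153 − 137 = 16 planned drop-outs per arm. The documents give no re-intervention or responder rate, so every rate below is an assumption.

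**Failures without a 12-month DIOP.** Let r be the responder rate among subjects with data, and f the share of failures without data among those subjects and these failures together. Counting the failures as non-responders gives r(1 − f), so the available-data rate is too high by r × f.

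| r | f = 2% | f = 5% |
|---|---|---|
| 60% | 1.2 points | 3.0 points |
| 70% | 1.4 points | 3.5 points |

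In counts, with exact 95% intervals:

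- Available data: 89/137 = 65.0% (56.4 to 72.9).
- With 3 failures added (3/140 = 2.1%): 89/140 = 63.6% (55.0 to 71.5).
- With 7 failures added (7/144 = 4.9%): 89/144 = 61.8% (53.3 to 69.8).

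At f = 10% the overstatement would be 6.0 to 7.0 points. That is an extreme case: 15 added failures (15/152 = 9.9%) would make nearly all of the 16 planned drop-outs per arm re-interventions.

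**Late re-interventions counted as responders.** The visit heading in 8.4.6 reads "MONTH 12 (DAYS 330 TO 420", so the window opens at day 330. Follow-up lasts at least one month after re-intervention, and 330 − 30 = day 300. An eye re-intervened from about day 300, or earlier if the adverse event persists, may still be in the study. Each such eye counted as a responder adds 1/137 = 0.73 points. Both effects together: 3 missing and 1 late gives 88/140 = 62.9%; 7 missing and 2 late gives 87/144 = 60.4%, against the reported 65.0%.

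**Between-arm difference.** The shift is r1·f1 − r2·f2.

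- Same r, failures 5% against 5%: 0.
- Same r, failures 5% against 2%: 0.60 × 0.03 = 1.8 to 0.70 × 0.03 = 2.1 points.
- Sign reversed: 0.40 × 0.05 = 2.0 points in one arm and 0.65 × 0.04 = 2.6 in the other, so the arm with fewer failures gains 0.6.

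The 95% half-width for a difference at 137 per arm is 1.96 × √(2r(1 − r)/137), which is 11.6 points at r = 60% and 10.9 at r = 70%. The shifts above are well inside it.

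**Percent change.** If the mean is −20% to −30% among subjects with data and failures are assigned 0%, the mean moves toward zero by |m| × f: from 20 × 0.02 = 0.4 to 30 × 0.05 = 1.5 percentage points.

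**What the 8.7 rule implies.** Inclusion criterion 5 requires a baseline unmedicated DIOP of at least 22 mmHg. Baseline carried to month 12 gives 0% change and a value above 18 mmHg, a non-response on both binary endpoints.

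**The case against.** The strongest reply is that 8.7 already settles the binary endpoints: a treatment failure for the effectiveness evaluation is naturally a non-responder, and the next sentence only adds the number that a continuous endpoint needs. That is a fair reading. On it the responder figures above do not arise, and only the wording of 10.4.4 needs to change. But 10.4.4 does not say it, and its stated data rule points the other way.

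For percent change, it can be argued that 10.4.4 does state a rule, and that the contrast with 10.4.3 shows a deliberate split between an imputed primary analysis and as-observed exploratory ones. That may be the intent. If so, 8.7 should say that its failure rule is confined to the primary endpoint. The picture is not clean, since 10.4.3 also plans plots of percent change in a section that opens with the primary imputation.

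The redactions limit the point. Section 10.4.2 refers to subjects without a 12-month washed-out DIOP "due to any reasons other than the first four criteria listed in Section" 10.4.1, so at least four criteria stand in text that cannot be read. A reader might infer that the plan has no rule for re-intervened subjects on these endpoints. The documents support only that none is stated in the readable text.

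The late-responder route is narrow. Standard-of-care follow-up makes an unmedicated three-timepoint DIOP possible, not certain.

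The effect is also small. Re-interventions are a safety endpoint in 6.2, so a reader could bound it, although the reported rates and intervals would not include it.

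**Conclusion.** The point holds as an inconsistency between 10.4.4 and 8.7 in the readable text. If 10.4.4 is applied literally, each arm's responder rate is overstated by about 1.2 to 3.5 points, assuming 60-70% response and 2-5% failures without data. Late re-interventions counted as responders would add 0.73 points each. The percent-change figures also rest on assigning failures exactly 0%.

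Some stronger readings are not supported:

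- That the primary endpoint or study success is affected. Section 8.7 gives the primary endpoint its own rule, and the endpoints at issue are exploratory.
- That the comparison is tilted toward a particular device. The shift can be zero or take either sign.
- That imputing these subjects would make percent change cover the same subjects as the primary mean change. The primary handling appears to involve at least four criteria in redacted text, so this cannot be verified.
- That the change in number of medications is biased in the same way. A withdrawn failure may lack that value too, but neither the size nor the direction of its change can be taken from the documents.

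Severity: CONSIDER.

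**What to change.** Reconcile 10.4.4 with 8.7.

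1. State in 10.4.4 that subjects with a secondary IOP-lowering intervention before the 12-month DIOP count as non-responders on both the ≥20% and the 6 to 18 mmHg endpoints, whether or not a DIOP is available.
2. For percent change, apply the sponsor's own 8.7 baseline imputation (0% change) to these subjects, and keep the available-data result as a sensitivity analysis.
3. Report per arm the number of failures with and without a 12-month DIOP.

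If the failure rule is meant for the primary endpoint only, say so in 8.7 and label the 10.4.4 results as applying to subjects with a 12-month DIOP. If the redacted text already has the rule, a cross-reference in 10.4.4 is enough.

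The cost is about one paragraph of text and no new data. Reported rates become slightly lower. Assigning 0% change is a single imputation, which is why the available-data result should stay beside it.

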1 PROTOCOL SYNOPSIS

Protocol Title	A Prospective, Randomized, Multicenter Study to Compare the Safety and Effectiveness of the OMNI® Surgical System and the iStent Inject in Pseudophakic Eyes with Open Angle Glaucoma- The TRIDENT European Trial
Study Device	OMNI Plus Surgical System (OMNI Surgical System)
Study Objectives	First, to compare safety and effectiveness outcomes for canaloplasty and trabeculotomy using the OMNI Surgical System to implantation of the iStent inject in lowering intraocular pressure (IOP) in pseudophakic eyes with open angle glaucoma (OAG), and second, to compare safety and effectiveness outcomes for canaloplasty alone (using the OMNI Surgical System) to implantation of the iStent Inject in lowering IOP in pseudophakic eyes with OAG.
Study Design	This is a prospective, randomized, multicenter, parallel group, comparative postmarket study in which a total of 459 subjects will be randomized in an equal allocation ratio (1:1:1) to either the OMNI (canaloplasty AND trabeculotomy), OMNI (canaloplasty only), or iStent inject and followed for 12 months after surgery.
Study Population	Pseudophakic adults with OAG.
Primary Effectiveness Endpoint	
Mean change in unmedicated DIOP from baseline at the 12-month postoperative examination 
The study hypotheses success will be evaluated using the primary effectiveness endpoint

OMNI System in Pseudophakic Eyes
Protocol 07062 Rev F

Other Effectiveness Endpoints	
• Proportion of eyes with a $\geq 20\%$ decrease in unmedicated mean diurnal IOP (DIOP) from baseline at the 12-month postoperative examination• Proportion of eyes with unmedicated mean DIOP between 6 and 18 mmHg inclusive at the 12-month postoperative examination• Mean change in the number of ocular hypotensive medications at the 12-month postoperative visit compared to Screening• Percent change in unmedicated DIOP from baseline to 12 months• Change in Ocular Surface Disease Index (OSDI) and Glaucoma Quality of Life (GQL-15) scores from screening at 12 months. 
These are the exploratory endpoints and will not be used to evaluate the study success.

Safety Endpoints	
• Rates of ocular adverse events (intraoperative, postoperative)• Reduction in best corrected distance visual acuity (BCDVA) from screening.• Secondary Ocular Surgical Interventions, including laser, for IOP control

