7 STUDY SELECTION CRITERIA

7.1 INCLUSION CRITERIA

For inclusion in this study, subjects must meet all the following criteria (only one eye of each subject is eligible, and all ocular criteria apply to the study eye only unless otherwise indicated):

1. Male or female subjects, 18 years or older
2. Pseudophakic. History of uncomplicated cataract surgery and posterior chamber IOL implantation without compromise to the lens capsule, zonular dehiscence/rupture or vitreous prolapse, [REDACTED].
3. Diagnosis of open angle glaucoma (POAG) including pigmentary and pseudoexfoliation substantiated using funduscopic exam (or OCT) and at least one reliable visual field test with the Humphrey automated perimeter using the SITA Standard 24-2 testing algorithm or an Octopus perimeter program G1 or G1X. Mean deviation score must be ≥ -12.0 dB (Humphrey) or ≤ 12.0 dB (Octopus). The visual field test may be historical (within 6 months prior to Screening Visit). If needed, visual field testing may be repeated between the Screening Visit and the Baseline Visit.
4. At the Screening visit, on 1-5 ocular hypotensive medications (fixed combinations counted as number of components) with a medicated IOP of ≤ 33 mmHg.
5. At the Baseline visit, unmedicated DIOP of ≥ 22 mmHg (≥ 24 mmHg for at least one timepoint and no less than 21 mmHg at any time point) and ≤ 36 mmHg and ≥ 3 mmHg higher than the medicated IOP at the Screening visit.
6. Scheduled for ab-interno minimally invasive canal-based glaucoma surgery.
7. Shaffer grade of ≥ 3 in all four quadrants
8. Able and willing to comply with the protocol, including all follow-up visits.
9. Understands and signs the informed consent.

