Subjects who meet all screening eligibility criteria will be instructed to discontinue their ocular hypotensive medication regimen, and to return for a Baseline visit after completing the appropriate washout period.

All subjects on ocular hypotensive medication(s) at Screening and Month 12 will be instructed to undergo a washout prior to the Baseline or Month 12 postoperative visit, respectively. If the study subject fails to remember to not use ocular hypotensive medication for the study eye per the required washout period, they can be re instructed and restart the washout. If deemed necessary by the PI, a subject can be given hypotensive medications after the baseline visit until the day of surgery. An oral hypotensive medication can be used between baseline to surgery. The minimum washout periods are specified in Table 2 below.

NOTE: A safety IOP check mid-way through the wash-out period may be performed at the Investigator's discretion where warranted to ensure subject safety.

Table 2: Ocular Hypotensive Medication Washout Periods

Brand Name/Chemical Name	Minimum washout period
Carbonic Anhydrase Inhibitors	
Diamox® (Acetazolamide) – oral Rx	5 days
Neptazane® (Methazolamide) – oral Rx	5 days
Azopt® (Brinzolamide)	5 days
Trusopt® (Dorzolamide Hydrochloride)	5 days
Muscarinic Agonists	
Salagen, Pilocar (Pilocarpine)	5 days
Alpha Adrenergic Agonists	
Alphagan® (Brimonidine)	14 days
Iopidine® (Apraclonidine Hydrochloride)	14 days
Beta Blockers	
Betagan® (Levobunolol Hydrochloride)	28 days
Betoptic® (Betaxolol Hydrochloride)	28 days
OptiPranolol® (Metipranolol)	28 days
Timoptic/Betimol® (Timolol Maleate)	28 days
Prostaglandin Analogs	
Lumigan® (Bimatoprost)	28 days
Travatan® (Travoprost)	28 days
Xalatan® (Latanoprost)	28 days
Zioptan® (Tafluprost)	28 days
Vyzulta® (Latanoprostene Bunod)	28 days
Rho Kinase Inhibitor	
Rhopressa® (Netarsudil)	28 days
Fixed Combination Medications	
Combigan® (Brimonidine Tartrate/Timolol Maleate)	28 days
Cosopt® (Dorzolamide Hydrochloride/ Timolol Maleate)	28 days
DuoTrav® (Travoprost/Timolol)	28 days
Ganfort® (Bimatoprost/Timolol)	28 days
Rocklatan® (Netarsudil/Latanoprost)	28 days
Simbrinza® (Brinzolamide/Brimonidine Tartrate)	28 days
Xalacom® (Latanoprost/Timolol)	28 days
Krytantek (Brimonidine Tartrate/ Dorzolamide Hydrochloride/ Timolol Maleate)	28 days
Other	Contact Sponsor

8.4.2 BASELINE VISIT (9:00 AM \pm 1 HR, NOON \pm 1 HR, 4:00 PM \pm 1 HR)

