10.2.2 As TREATED

The Intent to Treat (ITT) analysis population will include all subjects randomized and grouped according to their randomization assignment (as randomized) regardless if they actually undergo the assigned procedure. The As Treated (AT) population consists of the subjects that actually undergo the assigned procedure and will be grouped according to their actual treatments. For this study, the AT population will be used for the primary analyses of the primary and other effectiveness endpoints. The effectiveness analyses may be performed for the ITT population if needed.

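### Exploratory endpoints (section 10.4.4): the visible ANOVAs for change in medication count and percent change in DIOP omit the starting value and site; adjusting would be a cost-free gain in precision, possibly nil

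*Combined protocol and SAP*

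**What the plan says.** For change in medication count from screening to 12 months, section 10.4.4 states: "The ANOVA with study treatment group (three groups) as the factor will be used to compare the mean difference". Dunnett's test then compares each OMNI group with iStent inject. For the second endpoint it adds: "The same methods will be used to analyze the percent change in unmedicated DIOP from baseline to 12 months". The visible text names no screening count, baseline DIOP or site term.

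All three are available. Inclusion criterion 4 in section 7.1 requires subjects to be "At the Screening visit, on 1-5 ocular hypotensive medications", criterion 5 sets limits on baseline unmedicated DIOP, and section 5.2 stratifies randomisation by site.

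The status of these analyses is clear. Section 10.4.4 says "The analyses described in this section are exploratory in nature", and the synopsis says of the endpoints: "These are the exploratory endpoints and will not be used to evaluate the study success".

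Section 10.4.3 does list baseline DIOP, screening medication count and site. It tests them one at a time, for the primary endpoint only, as prognostic checks at p = 0.15. For percent change it gives a scatter plot against baseline DIOP, and box plots by covariate category except site. None of this is an adjusted treatment comparison for the two endpoints discussed here.

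Section 10.4.1, the end of section 10.4.4 and section 10.4.5 are redacted.

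**The concern.** A subject on one drug can lose at most one, and a subject on five can lose five. Part of the spread in medication change may therefore only reflect where subjects started. A model with treatment as its only factor leaves that spread in the error term. Standard errors are then larger than they need be, and a modest difference between devices is easier to miss. The same could hold, to a lesser degree, for percent DIOP change and for differences between sites. Only precision on exploratory comparisons is at stake; study success is not.

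**Working it through.** **The plan's own figure.** 137 / 0.90 = 152.2, rounded up to 153 per group; 3 × 153 = 459. This matches sections 1 and 5.1. The visible text does not show how 137 was derived, so 137 per group is taken as given.

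**Assumptions.** The documents give no SDs, correlations, effect sizes or site variance. Screening count is assumed to take the values 1–5 with probabilities 0.28, 0.34, 0.24, 0.10, 0.04. The mean is then 2.28, the mean square 6.40 and the variance 6.40 − 2.28² = 1.20 (SD 1.10). The critical value is 2.23, about Dunnett's for two comparisons at 5% overall; the visible text states no level for these tests.

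**Medication count: what drives the gain.** Let X be the screening count, Y the 12-month count and b the slope of Y on X. The variance of Y − X that adjustment removes is (1 − b)² × Var(X). It vanishes at b = 1 and grows as b falls.

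*Independent dropping.* Each drug is kept with probability q, so b = q and Var(Y − X) = (1 − q)² × 1.20 + q(1 − q) × 2.28.
- q = 0.5: 0.300 + 0.570 = 0.870; screening count explains 0.300/0.870 = 34%.
- q = 0.4: 0.433 + 0.547 = 0.980; it explains 44%.
- Effect: 0.10 × 2.28 = 0.228 medications.
- Unadjusted: mean variance 0.925, SE = √(2 × 0.925/137) = 0.116, 0.228/0.116 = 1.96, power Φ(1.96 − 2.23) = 39%.
- Adjusted: mean residual variance 0.559, SE = 0.0903, ratio 2.52, power 62%.

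Simulation (4,000 trials of 3 × 137) gives 40% and 61%.

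*All-or-none dropping.* A subject keeps every drug with probability q or none. Again b = q, but Var(Y − X) = (1 − q) × 6.40 − (1 − q)² × 2.28².
- q = 0.5: 1.900; q = 0.4: 1.969; screening count explains 16% and 22%.
- Unadjusted: mean variance 1.935, SE 0.168, ratio 1.36, power 19%.
- Adjusted: mean residual variance 1.568, SE 0.151, ratio 1.51, power 23%.

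Simulation gives 19% and 22%.

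*Simulated power, unadjusted vs adjusted, for a 10-point difference in retention:*

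| Dropping pattern | 50 vs 40% | 35 vs 25% | 70 vs 60% |
|---|---|---|---|
| Independent | 40 vs 61% | 36 vs 69% | 55 vs 66% |
| Moderately clustered | 32 vs 44% | 29 vs 51% | 42 vs 50% |
| Strongly clustered | 26 vs 34% | 25 vs 40% | 34 vs 38% |
| All-or-none | 19 vs 22% | 19 vs 26% | 25 vs 27% |

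*Stepwise reintroduction* (half of control subjects drug-free at 12 months; need for drugs shifted by 0.3 SD):

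| Slope of 12-month on screening count | Unadjusted | Adjusted |
|---|---|---|
| 0.17 | 20% | 40% |
| 0.42 | 30% | 44% |
| 0.72 | 49% | 55% |
| 0.96 | 73% | 74% |

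Across all models screening count explains 0–68% of the variance. With no true difference, both methods reject 2.3–3.0% per comparison (nominal about 2.6%), so the gain does not come from extra false positives.

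*Larger effect.* For a 20-point difference (0.456 medications), unadjusted power is 92–99% (independent) or 80–90% (strongly clustered). All-or-none was not simulated here. The formula above at 50 vs 30% gives variances 1.900 and 1.933, SE 0.167, power 69%; adjusted, residual variances 1.600 and 1.344, SE 0.147, power 81%.

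*Closed-form cross-check.* With r = SD at 12 months / SD at screening and correlation ρ, the variance ratio is r²(1 − ρ²)/(1 + r² − 2ρr).
- r = 1: 0.60, 0.70, 0.80 at ρ = 0.2, 0.4, 0.6. Intervals are 22%, 16% and 11% narrower.
- r = 1.25: intervals are 15%, 8% and 3% narrower.

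**Percent DIOP change.** Dividing by baseline already removes much of the dependence.
- Baseline SD about 2.4 mmHg within 22–36, 12-month SD 4, 12-month mean 16–20: intervals 0–4% narrower at ρ = 0.2–0.6, and at most about 9% narrower over ρ = 0–0.7.
- Wider assumptions: baseline explains 0–11% of variance at slopes 0.4–1.0, 3–16% at slope 0.2, and 6–28% only if 12-month DIOP is unrelated to baseline.

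**Site** (24 or 26 sites, blocks of 6, about 10% dropout). The ratio of adjusted to unadjusted SE is 1.006–1.007 if sites do not differ, 0.98 at a 5% site share of variance and 0.96 at 10%.

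**The case against.** The strongest case against is that nothing here is wrong. ANOVA with Dunnett's test is valid under randomisation, the endpoints are exploratory, and the visible text sets no power target for them. That stands, and it limits the point to an improvement.

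The size is also unknown. Every figure beyond 137 per group rests on assumptions, and the range includes zero. The 10-point scenario is a small effect that no document names as of interest; for a 20-point difference the plain ANOVA has 80–99% power in the two models simulated. This stands too.

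A reader might infer that the drug rules themselves imply a loss: subjects on drugs "will be instructed to undergo a washout prior to the Baseline or Month 12 postoperative visit", and section 8.6 reintroduces the preoperative classes. The documents do not support that. A closer tie between 12-month and screening count moves the slope towards 1, which shrinks the gain for a change score.

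A reader might also infer that the trial plans no adjusted analysis of these endpoints, or none of the primary endpoint. The redactions rule out either conclusion; section 10.4.5 is listed in the contents as additional effectiveness analyses and could hold one.

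What the objection does not remove is that the covariates are already collected, and that adjustment costs almost nothing when they turn out not to matter.

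**Conclusion.** The point holds as a low-severity, cost-free improvement to the visible text of section 10.4.4. It matters mainly for medication count, where the gain is material if the slope of 12-month on screening count is well below 1, as when eyes shed a share of their drugs, and nil if the slope is near 1. For percent DIOP change the gain is usually 10% of variance or less and often near zero. Site gives standard errors about 0–4% smaller at a 0–10% share of variance, and costs under 1% if sites do not differ.

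A reader might take the omission as a source of bias or false positives; it is neither. A separate question, not assessed here, is the analysis set: these analyses "will be based on the available data of the AT population", and section 10.2.2 says "For this study, the AT population will be used for the primary analyses of the primary and other effectiveness endpoints". Covariate adjustment is not offered as a remedy for that. The responder comparisons in section 10.4.4 are also outside this point.

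**What to change.** In section 10.4.4, unless the redacted text already provides it, make the comparison of medication-count change an ANCOVA with treatment, screening count as a continuous covariate, and site (as a random effect, or with small sites pooled by a rule fixed in advance). Keep the two Dunnett comparisons with iStent inject, now on the adjusted means. Use the same form for percent DIOP change, with baseline DIOP as the covariate; this is a minor gain.

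The cost is a few lines of SAP text and minor programming. No subjects, visits or measurements are added.
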